They will also be provided a comprehensive exercise safety orientation which is detailed in Appendix 22a. Briefly, the information includes review of devices, supplies, space, safe glucose ranges and carbohydrate snacking for exercise, reminders from CGM training pertinent to exercise, insulin adjustments around exercise, watching for symptoms, and who to call with concerns. They will be provided and instructed to keep carbohydrate-containing foods and drinks (eg, orange juice, glucose tablets) available to use when indicated by glucose testing or symptoms. In addition, they will be educated regarding the American Diabetes Association guidelines for self-monitoring blood glucose and urine ketones, if indicated, and appropriate adjustments of diet and insulin before, during, and after engaging in exercise. For instance, if blood glucose is less than 90 mg/dL, they can consume 10-20g of fast-acting carbohydrates (eg, 4 oz of orange juice or 3 glucose tablets) and wait to commence with exercise until blood glucose is confirmed to be above 90 mg/dL. If blood glucose is greater

Protocol Number 2000035846

August 13, 2024 Version #7

than 270 mg/dL and not associated with a recent meal, they must check their blood for ketones and avoid exercise if they have ketones ≥1.0 mmol/L.

Participants will be encouraged to be vigilant for symptoms of hypoglycemia during exercise and for the remainder of the day because exercise increases the risk for nocturnal hypoglycemia. The symptoms they will be encouraged to be vigilant for include cold, clammy skin, pallor, difficulty concentrating, shakiness, lack of coordination, irritability, hostility, and poor behavior, a staggering gait, fatigue, nervousness, excessive hunger, headache, blurred vision and dizziness, and abdominal pain or nausea. In these instances, they will be advised to refrain from exercise while checking blood glucose.

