Participants will be monitored for exercise-associated events (hypo- and hyperglycemia, diabetic ketoacidosis, other health risks) as detailed in the Data and Safety Monitoring Plan (Sect 8.7). In brief, a research staff member will daily review each participant's CGM data, fingerstick glucose tests, ketone tests, exercise start times, and diary records of hypoglycemia and other clinical events (see Data and Safety Monitoring Plan "Tracking" section) each of the first 14 days of the trial for each participant. Instances of severe hypoglycemia, diabetic ketoacidosis, a missed ketone test, or other clinical event will result in immediate discontinuation of exercise until a physician has alerted the participant and the participant's primary diabetes care provider to the issue and developed a prevention strategy, consulting with the primary diabetes care provider as needed. For instances of a missed test, physician contact can be replaced initially by research assistant contact to query symptoms and troubleshoot testing procedures, followed by physician contact if symptoms were present.

The principal investigator [name] and a study physician (Drs. [name] or [name]) will review the above data plus carbohydrate and insulin dosing around exercise, every 2 weeks during the clinical trial. Participants exhibiting patterns confirmed by the physician to be indicative of problematic exercise-induced hypo- or hyperglycemia will be alerted to the issue and referred to their diabetes care provider for follow-up (all patients will submit provider information to the study team at study start). [name] will join at least every other occurrence of these meetings (i.e., at least every 4 weeks) and provide a second review of [name] medical management decisions. Participants will be trained in allowing their provider to access their CGM data. Mild hypoglycemia will not be exclusionary since such individuals are in high need of exercise intervention. Any day-to-day decisions about clinical care, including adjustment of insulin dosing or CGM target ranges will be made by the participant's provider, not the study physicians. Clinical providers will not monitor CGM in real-time.

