All participants participate in routine follow-up, consisting of quarterly visits to the clinic and 24-hour access to nurse and/or physician consultation. It is not anticipated that any of the data collection procedures or the intervention will cause any adverse effects. Nonetheless, the participants will continue to receive routine medical and nursing care throughout the study period, and intervention for adverse effects will be available.

These protocols have been utilized by Drs. [name], [name], and [name] over four prior exercise clinical trials among youth and adults with T1D that had no instances of severe hypoglycemia or diabetic ketoacidosis (HIC #s 1605017843, 2000025992, 2000030105, 2000033736).

**Hyperglycemia:** There is a risk of hyperglycemia due to exercise from factors such as counterregulatory hormone response releasing glucose into the blood.

See above regarding blood glucose testing, blood glucose monitoring review by research staff, Drs. [name], [name], [name], and routine clinical support. Regarding hyperglycemia

August 13, 2024 Version #7

specifically, participants will be encouraged to be vigilant before, during, and after exercise for signs or symptoms of hyperglycemia such as dry mouth, headache, heaviness, pressure behind the eyes, or unusual increase in thirst. They will be advised in these instances to reassess their blood glucose. If blood glucose is greater than 270 mg/dL and not associated with a recent meal, they should check their blood for ketones and avoid exercise if they have ketones ≥1.0 mmol/L.

**Severe hypoglycemia and hyperglycemia:** There is a risk of severe hypoglycemia or hyperglycemia due to exercise.

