Severe hypoglycemia will be defined as any blood glucose level resulting in symptoms which require outside intervention to control (including but not limited to confusion and loss of coordination). Severe hyperglycemia will be defined as blood glucose >500mg/dL, presence of urine ketones or other signs and symptoms of diabetic ketoacidosis (including but not limited to weakness and fatigue, confusion, shortness of breath). Patients will be asked to contact emergency services should these events occur. Specifically, Yale-affiliated patients with T1D have access to a 24-hour hotline with access to nurse and/or physician advice or can choose to call 911. Non-Yale-affiliated patients will be asked to call 911 or contact their providers' after-hours staff (all patients will submit provider information to the study team at study start). The study team will be notified of the event within 24 hours via daily diaries; moreover all participants will have the PI's direct contact information should they choose to contact him earlier by phone or email. Our team will then notify the patient's primary diabetes provider (if not already notified) and all study-related exercise will be suspended until patient receives further advice from their diabetes provider regarding next steps which may include modified exercise routines or suspension of the study altogether. All serious adverse events such as severe hypoglycemia and hyperglycemia will be reported to the PI verbally within 24 hours of study staff being notified and to university's IRB committee in writing within 5 business days. In the case of >1 episode of severe hypoglycemia or 1 episode of diabetic ketoacidosis not closely related to pump site failure, the participant will be removed from the study and referred to their diabetes care provider for follow-up.

**Exercise-related injuries:** Exercise may cause muscle soreness/pain, muscle strain, cardiovascular events, and tiredness during or after the activity.

The probability and magnitude of such injuries varies based upon factors such as the individual participant's fitness level and the difficulty of the exercise routines. Our previous pilot studies (sect. 1.2) had no injuries or muscle strains. The American Heart Association Scientific Statement notes that the frequency of exercise-related out-of-hospital cardiac arrest among the general population ages 35-90yr was measured at 3.0 per 100,000 person-years.

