Daily morning survey that captures daily morning context during app intervention is started at this visit -- Appendix 8a: 1) prior day hypoglycemia episodes; 2) recent clinical events (asked every day for 2 weeks, then every 2 weeks); 3) fear of hypoglycemia previous night and coming day; 4) sleep quality and nocturia previous night; 5) competing demands and exercise plan for the day.

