# **Tracking**

A. Daily monitoring during first 2 weeks for ketoacidosis, severe hypoglycemia, and other health risks associated with exercise:

We will detect any diabetic ketoacidosis or severe hypoglycemia within 24hr and suspend exercise until a personalized preventive strategy can be formed. To achieve this level of monitoring, a research assistant will monitor daily the biometric dashboard which contains Bluetooth-captured glucose, ketones, and exercise start/stop times. Safety signals include any of the following during or within 1hr of exercise: 1) Diabetic ketoacidosis (glucose ≥270 mg/dL + ketones ≥1.0 mmol/L), 2) Possible diabetic ketoacidosis (glucose ≥270 mg/dL and failure to test ketones), and 3) Possible severe hypoglycemia (glucose <55 mg/dL). Research staff will respond to each of these events within 24hr of its occurrence by informing the participant to immediately suspend the exercise program (app account will be suspended) until the participant has been contacted by a study physician. The physician will alert the participant and the participant's primary diabetes care provider to the issue and develop a prevention strategy, consulting with the primary diabetes care provider as needed. The exercise suspension will then be lifted, unless the participant has met the protocol's stoppage criteria (>1 episode of severe hypoglycemia, 1 episode of diabetic ketoacidosis not closely related to pump site failure).

In the event of the "possible" occurrences (#2, #3), physician contact can be replaced initially by research assistant contact to query symptoms. Then, if possible diabetic ketoacidosis is supported by the participant reporting symptoms, or possible severe hypoglycemia is supported by the participant reporting altered mental and/or physical status requiring assistance from another person for recovery, physician contact will be required as in paragraph #1 above.

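### Read literally, the two-week daily safety window closes before app exercise starts on Day 22 and covers none of its 28 days

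*Combined protocol and SAP*

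**What the plan says.** Section 8.7, Tracking A, is titled as daily monitoring for the first two weeks but does not say two weeks from what. It lists three signals occurring during exercise or within an hour of it. The first is "Diabetic ketoacidosis (glucose ≥270 mg/dL + ketones ≥1.0 mmol/L". The other two, a missed ketone test at high glucose and a glucose below 55 mg/dL, are called possible events. The response suspends the app account until the participant has been contacted. The same part undertakes to find any other exercise-related health risk within 24 to 36 hours, through a morning survey question on clinical events that is asked and monitored daily.

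The timing is set elsewhere:

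- 2.2 Risks: staff review glucose, ketones, exercise times and diary records daily for "each of the first 14 days of the trial for each participant". The principal investigator and a study physician "will review the above data plus carbohydrate and insulin dosing around exercise, every 2 weeks during the clinical trial".
- 6.1.1, Visit 2 (Day 8): the morning survey begins, and its clinical-event item is "asked every day for 2 weeks, then every 2 weeks".
- 6.1.1, Visit 4 (Day 22), Data Captured by App: the same item is asked every two weeks only.

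On ketones, section 2.2 says that participants whose glucose is above 270 mg/dL must act as follows if it is "not associated with a recent meal, they must check their blood for ketones and avoid exercise if they have ketones ≥1.0 mmol/L". Tip B under Table 3 accepts blood or urine, gives no cut-off, and after a positive test advises against vigorous activity only.

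On removal, section 2.2 states that after "1 episode of diabetic ketoacidosis not closely related to pump site failure, the participant will be removed from the study". Section 6.5 lists the same criterion among the grounds on which researchers may withdraw someone.

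**The concern.** Participants enter sedentary (fewer than 1.0 exercise sessions per week) and receive the exercise app only at Visit 4. The signals in section 8.7 are defined around exercise, and the response is to suspend the app. A two-week window counted from consent or from Visit 2 would therefore watch people before study exercise begins, and would step down when the added risk starts. An injury, cardiac symptom or metabolic event in the first app weeks could then be found days later than section 8.7 undertakes.

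Tip B raises a smaller safety question. A participant with blood ketones of 1.0 mmol/L or more who follows it could still do light or moderate exercise, which section 2.2 rules out.

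**Working it through.** The plan gives no coverage figure to reproduce, so the check counts days.

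**Inputs** (Table 1 and the visit descriptions in 6.1.1): Visit 1 on Day 1, Visit 2 on Day 8, Visit 4 and app start on Day 22, Visit 8 and the end of the 4-week intervention on Day 50. Visits 2 to 10 may move by ±7 days.

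**App days:** Day 22 to Day 49, so 49 − 22 + 1 = 28.

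**Overlap of each candidate 14-day window with the app days:**

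| Window starts at | Source | Days | App days covered |
|---|---|---|---|
| Trial start | 2.2 Risks | 1–14 | 0 of 28 |
| Visit 2 | Visit 2 text, clinical-event question | 8–21 | 0 of 28 |
| App start | implied by 8.7 and Tool #2, not stated | 22–35 | 14 of 28 |

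**Earliest Visit 4** (22 − 7 = Day 15, with Visit 2 kept on Day 8): app days become 15–42.

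- Days 1–14 still overlap by 0.
- Days 8–21 overlap on Days 15–21, so 21 − 15 + 1 = 7 days. This uses the Visit 2 wording. The Visit 4 wording, every two weeks once the app is in use, would give none.

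**Detection time.** Section 8.7 promises 24 to 36 hours. In the app phase the clinical-event item comes every 14 days. The next scheduled contact that could pick up an event is the weekly symptom check (Visits 5 to 8, nominally Days 29, 36, 43 and 50), at most 7 days away. An event that is neither a hypoglycemia episode nor volunteered by the participant could therefore wait up to about 7 days, against 1.5.

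**Ketone advice side by side:**

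| | Section 2.2 | Tip B |
|---|---|---|
| Glucose trigger | above 270 mg/dL | above 270 mg/dL |
| Recent-meal exception | yes | no |
| Sample | blood | blood or urine |
| Ketone cut-off | 1.0 mmol/L or more | any positive |
| Action | avoid exercise | avoid vigorous activity |

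Tip B is stricter on when to test and looser on what to do after a positive result. Only the second difference reduces protection.

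**The case against.** The strongest reply is that the authors meant the window to start with the app. Supplies are mailed after Visit 1 and set up at Visit 2, so Days 1–7 yield no data from newly issued study devices and the Section 2.2 wording is hardly workable. The section 8.7 signals presuppose exercise and an app account. Tool #2 describes staff viewing the dashboard daily for safety during the messaging phase. There are also backstops: the weekly symptom check and adverse-event query, the morning item on hypoglycemia, daily monitoring of the diaries (7.6), the two-weekly physician review, and direct access to the principal investigator.

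Most of this stands as evidence of intent. It does not repair the text. The clinical-event question is the tool section 8.7 relies on for 24-to-36-hour detection, and 6.1.1 places its daily phase explicitly before Visit 4. Reading the diary daily does not help if the item is not asked. Tip B belongs to a table titled as an example and is feedback after the fact, with safety orientation given before exercise. That lowers its weight, but it remains advice sent to participants.

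A reader might also infer that a symptom-free glucose and ketone pair automatically becomes a ketoacidosis episode and forces removal. The documents do not support that. The pair is in a list of triggers, study-physician contact comes before the stoppage criterion is weighed, and the criterion itself needs a judgement about pump site failure. Two-weekly endocrinologist review, an adverse-event report with corroborating records, and DSMB review follow. Section 2.2 lists "presence of urine ketones or other signs and symptoms of diabetic ketoacidosis" within its definition of severe hyperglycemia, and no stricter definition of an episode appears that the pair would fail. Whether the pair is clinically enough needs an outside source. What is missing is a sentence saying who decides.

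Nor is there a specified safety result for one counted episode to overturn. Section 2.2 cites four earlier trials "that had no instances of severe hypoglycemia or diabetic ketoacidosis", but section 4.2 lists no ketoacidosis or adverse-event outcome.

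**Conclusion.** The timing is wrong as written, and it concerns patient safety. Taken literally, daily review under section 2.2 and the daily clinical-event question under 6.1.1 cover 0 of 28 app days on the nominal schedule, and 7 for the question in the most favourable case computed. Counting from app start would give 14. The figures assume app use on Days 22–49 and Visit 2 on Day 8. They describe what the text requires, not what staff would do. With the backstops, the likely loss is delay in finding some events, not absence of monitoring. How many events would be affected cannot be derived from the documents.

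The tip B mismatch is real and should be corrected with it. The name of the first signal and the differing removal verbs are minor clarifications. The label errs towards suspending too readily, not towards less protection.

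**What to change.** 1. In 2.2, in the Visit 2 and Visit 4 texts of 6.1.1, and in 8.7 Tracking A, state that daily biometric review and the daily clinical-event question cover the first 14 days after app start (Visit 4). Keep the existing daily question from Visit 2 to Visit 4, since moving it would give up coverage on Days 8–21. The cost is about 14 more days of one survey item. Tool #2 already has staff on the dashboard daily.
2. Reword tip B so that it matches section 2.2: avoid exercise if blood ketones are 1.0 mmol/L or more. The cost is one sentence.
3. As a clarification, rename the first signal in 8.7 as a possible event, keeping immediate suspension and physician contact. Say that the study physician decides at that contact whether it counts as a ketoacidosis episode for the stoppage criterion. Use the same removal verb in 2.2 and 6.5. The cost is a few words and one line in a contact already required.

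### Glucose above 500 mg/dL is a serious adverse event that suspends exercise in Section 2.2, but the Section 8.7 dashboard signals and the exercise rules do not carry that threshold

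*Combined protocol and SAP*

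**What the plan says.** Section 2.2 (Severe hypoglycemia and hyperglycemia) gives the definition: "Severe hyperglycemia will be defined as blood glucose >500mg/dL, presence of urine ketones or other signs and symptoms of diabetic ketoacidosis". Read as alternatives, its items make glucose above 500 mg/dL sufficient alone. The consequence is that "all study-related exercise will be suspended until patient receives further advice from their diabetes provider". The notification route is "The study team will be notified of the event within 24 hours via daily diaries", and participants also hold the PI's direct contact details. On reporting, "All serious adverse events such as severe hypoglycemia and hyperglycemia will be reported to the PI verbally within 24 hours" of staff learning of them. Participants have their own instruction: "Patients will be asked to contact emergency services should these events occur".

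Section 8.7, Tracking A, is headed "Daily monitoring during first 2 weeks for ketoacidosis, severe hypoglycemia" and other exercise-associated health risks. It introduces its list with "Safety signals include any of the following during or within 1hr of exercise". Signal 1 is glucose of at least 270 mg/dL together with ketones of at least 1.0 mmol/L. The other two are "2) Possible diabetic ketoacidosis (glucose ≥270 mg/dL and failure to test ketones), and 3) Possible severe hypoglycemia (glucose <55 mg/dL"). Its 24-hour detection commitment names ketoacidosis and severe hypoglycemia only.

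The rules on starting exercise (Section 2.2, Hypoglycemia and Hyperglycemia) ask for a ketone test above 270 mg/dL when no recent meal explains the reading, and bar exercise at ketones of 1.0 mmol/L or more. Follow-up tip B under Table 3 (Section 6.1.1, Tool #3) tells a participant with high glucose, no ketones and no symptoms that exercise should be fine. None of these states an upper glucose limit.

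**The concern.** The low side has a signal that fires on glucose alone. On the high side both signals also need a ketone condition, so the limit that Section 2.2 treats as serious has no counterpart among the signals that staff are told to watch for. If such a reading fires no signal, the exercise hold waits for someone to report it or recognise it. Meanwhile the rules participants follow day to day allow exercise as long as ketones are low. At stake are the timing of the hold and the timing of reports to the PI, the IRB and the DSMB. No primary or secondary analysis is affected.

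**Working it through.** The plan gives no figure to reproduce. The check sets the provisions side by side.

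**1. Which readings above 500 mg/dL fire a signal?** Every such reading also meets the 270 mg/dL part of signals 1 and 2, so the outcome depends on ketones and timing. Around exercise means during it or within an hour of it.

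| Ketones | Around exercise | Any other time |
|---|---|---|
| At least 1.0 mmol/L | signal 1 | none |
| Not tested | signal 2 | none |
| Tested, below 1.0 mmol/L | none | none |

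Around exercise 2 of 3 cases fire; at other times 0 of 3. In total 2 of 6 fire and 4 do not. These are logical cases of unknown and unequal frequency.

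**2. Does the diary deliver 24-hour notification?** The morning survey starts at Visit 2 (day 8). As Section 6.1.1 lists its content, it asks daily about hypoglycemia and has no hyperglycemia item. The item that could capture a reading above 500 is the one on recent clinical events. Under Visit 2 it is asked daily for two weeks and then every two weeks, so daily asking nominally ends on day 8 + 14 = day 22, when the app starts. Under Visit 4 (Data Captured by App) it is two-weekly only. In the app phase the asking interval is therefore 14 days, against an intended 24 hours. The 24 to 36 hour route in Section 8.7 uses the same question.

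**3. What other routes remain on exercise days?** The Table 1 footnote targets exercise in intervention and follow-up: 6 × 7 = 42 days, nominally days 22 to 64.

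- Daily device-data review for the first 14 days (Section 2.2). Counted from day 1 or day 8 it overlaps 0 of 42 days; counted from app start, 14/42 = 33%.
- Daily dashboard check in the app phase (Section 6.1.1, Tool #2), days 22 to 50: 28/42 = 67%. It refers back to Section 8.7 Tracking for what to look for.
- Follow-up, days 50 to 64: 14/42 = 33%. No daily device check is clearly stated.
- Adverse event enquiry at Visits 2 to 10 (Table 1): nominally every 7 days.
- Device-data review that includes adverse events (Section 8.7, Tracking B): every 14 days.

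All days are nominal, since visits have windows of ±7 days.

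**4. Do the exercise rules agree with the suspension?** Section 2.2 suspends study exercise above 500 mg/dL whatever the ketones. The two ketone rules and tip B set no ceiling when ketones are below 1.0 mmol/L or absent. A participant at 510 mg/dL without ketones who feels well is suspended under one provision and told under tip B that exercise should be fine.

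**The case against.** The strongest reply is that the threshold is already written down. Section 2.2 states it, staff see device data daily at least in the app phase, its stop list includes other clinical events, the Section 8.7 list is introduced as inclusive rather than exhaustive, and Tracking B covers serious adverse events regardless of cause. Staff who apply the Section 2.2 definition to what they see would hold exercise. This stands, and it limits the point: what is missing is the threshold in the list they are told to work from.

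The sections also do not contradict each other on detection. Section 8.7 promises 24-hour dashboard detection only for ketoacidosis and severe hypoglycemia; Section 2.2 names the diary and direct contact for severe hyperglycemia. That stands too, but step 2 shows that the diary does not reliably do this in the app phase.

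It can be said that the specific suspension above 500 mg/dL overrides the general rules for readings above 270. That is the sensible reading, but a participant looking at tip B would not learn it from the tip.

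Three of the four silent cases lie away from exercise, where day-to-day care belongs to the participant's own provider, who receives a code to view CGM values. This reduces the risk. However, the Section 2.2 definition has no time limit, and Section 1.1 itself says exercise can disturb glucose for up to 24 hours.

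A reader might infer that a reading above 500 goes undetected, or that two weeks can pass before anyone asks. The documents do not support either. Signals 1 and 2 catch the reading around exercise unless ketones were tested and found below 1.0 mmol/L, participants are told to seek emergency help, and weekly visits enquire about adverse events. The 14-day interval applies only to the scheduled device-data review.

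**Conclusion.** The point holds as a coverage gap and a wording inconsistency, and the change is a cheap improvement. In four of the six logical cases no listed signal fires. Detection then rests on participant contact, on staff applying the Section 2.2 definition to data they see, on the weekly enquiry (nominally 7 days apart), or on the two-weekly device-data review. The exercise rules and tip B are inconsistent with the suspension in Section 2.2.

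The harm is possible delay in holding exercise and in reporting, not absence of protection. Its frequency cannot be derived from the documents, and 2 of 6 must not be read as a detection rate.

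The conclusion assumes that the items in the severe hyperglycemia definition are alternatives. It concerns the protocol text only: Appendix 8a (morning survey), 22a (safety orientation), 22b (exercise data monitoring) and the procedure manual are not in the documents and may already carry the threshold.

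**What to change.** Add a fourth signal to Section 8.7, Tracking A: *glucose >500 mg/dL (or the device's above-range reading, confirmed by fingerstick), any ketone result, at any time*. Attach the same suspension and physician contact as signal 1. State that it applies in the dashboard check already run daily in the app phase (Tool #2), and so is limited neither to the first two weeks nor to the time around exercise.

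In the two ketone rules of Section 2.2 and in tip B, say that exercise is withheld above 500 mg/dL regardless of ketones, in line with the suspension already stated.

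The cost is a wording amendment through the IRB, one more line in an existing check, and possibly a few extra exercise holds. The documents give no reporting range for the CGM or the meter; if a lower above-range reading has to serve as the trigger, there would be more holds. Carrying the daily check through follow-up to day 64 is optional. It would add up to 14 checks per participant, with at most 11 participants active at once.
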